4.3 PATIENT ELIGIBILITY/ INCLUSION AND EXCLUSION CRITERIA

Any individual with NF1 based on either NIH-diagnostic criteria or congenital pseudarthrosis of the tibia plus documented mutation in the *Nf1* gene is eligible for this study. Furthermore, decisions for surgical intervention must be made on a clinical basis with a determination that intramedullary rod plus autogenous bone graft is the most appropriate management approach for that individual patient. Patients may be enrolled only at the time of 1st or 2nd surgery for tibial pseudarthrosis, not subsequent surgeries. Candidates must be able to travel to an orthopedic surgical site that is participating in the study. Patient insurance must approve coverage of the surgical procedure and short-term post-operative care at the orthopedic center performing the operation, or patients can use a self-pay procedure to cover the surgical and hospital costs associated with the surgical procedure.

Inclusion Criteria for all patients:

- All patients who do not have a documented *NF1* mutation must meet the clinical diagnosis of NF1 using the NIH Consensus Conference criteria. In addition to tibial pseudarthrosis, one or more of the following diagnostic criteria for NF1 must be present:
 - Six or more café-au-lait spots ($\geq 0.5\text{cm}$ prepubertal; $\geq 1.5\text{cm}$ postpubertal)
 - Freckling in the axilla or groin
 - Optic pathway glioma
 - Two or more iris Lisch nodules
 - Two or more neurofibromas or one plexiform neurofibroma
 - A first-degree relative with NF1
- Patients must have tibial pseudarthrosis that has the potential to cause significant morbidity. Radiographic findings (AP & lateral leg radiographs) must support the diagnosis of tibial pseudarthrosis with chronic non-union.
- Age between 2 years and 18 years of age at time of study entry.
- Performance Level: Karnofsky $\geq 50\%$ for patients > 10 years of age and Lansky ≥ 50 for patients ≤ 10 years of age (Appendix III).
- Prior Therapy:
 - Patients who have undergone 1 previous surgery for tibial pseudarthrosis repair will be eligible to enter the study if they have refracture. Use of BMP-2 in the prior surgery is permitted, however patients with prior exposure must be screened for antibodies to BMP-2, bovine collagen, and rhBMP-2 neutralizing antibodies.

- Prior use of BMP-2 is allowed but will be recorded as a possible compounding factor.
- Patients who have had 2 or more prior surgeries for pseudarthrosis repair are ineligible

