A normal human serum pool and an antibody positive serum which recognizes and binds to rhBMP-2 (or bovine I collagen) are included on each plate as negative and positive controls, respectively, to monitor assay performance. The optical density (OD) values of the samples were compared to the cutpoint OD of the plate to determine if antibodies specific for rhBMP-2 or bovine I collagen were present or absent. The cutpoint OD was defined as two times the mean of the negative control OD. Samples were initially tested in duplicate in a screening format at 2 dilutions. Any samples that generated an OD greater than or equal to the cutpoint were

reanalyzed in the titer format. In the titration format, the same samples were also incubated on plates that were uncoated (no rhBMP-2 or bovine I collagen) to determine if a positive signal generated was specific or non-specific. The antibody titer was defined as the reciprocal dilution of the sample which generated an OD equal to the cutpoint OD. This was reported as the arithmetic antibody titer.

Antibody testing will be performed on serum samples at the following timepoints:

- Pre-operatively; 6 weeks \pm 2 weeks, 3 months \pm 2 weeks, 6 months \pm 4 weeks, and 12 months \pm 4 weeks post-op.
- Any subject testing positive to antibodies to bovine collagen will be tested for antibodies to human collagen.
- Any subject testing positive to antibodies to rhBMP-2 will be tested for BMP-2 neutralizing antibodies

Patients with history of prior exposure to BMP-2 in a previous surgery, who are positive for antibodies to rhBMP-2, bovine collagen, or neutralizing antibodies pre-operatively are excluded from participation in the study.

Radiographs of tibial union

Standard anteroposterior (AP) and lateral (lat) radiographs of the tibia and fibula will be obtained within 2 weeks prior to surgical intervention and postoperatively at the following intervals: 6 weeks (+/- 2 weeks), 12 weeks (+/- 2 weeks), 6 months (+/- 4 weeks), 9 months (+/- 4 weeks) and 12 months (+/- 4 weeks). Postoperative exams will be acquired out of cast.

The imaging protocol of the lower leg is standard anteroposterior and lateral radiographs of lower leg and ankle. Images will be sent on CD to the Radiography Review Panel at TSRH.

Tissue Collection for Future Studies (US Centers; Further details in Appendix II and Lab Manual)

The following tissue will be collected following participant consent:

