All statistical analyses will be performed using SAS (version 9.3). All analyses are based on evaluable patients, as defined in section 10.5 with sensitivity analyses considering inevaluable patients as failures (scores 4-7). Summary statistics will be used to describe the study population (such as ranges, medians of ages, gender, baseline performance characteristics). The quality of life assessment in this study is based on the Pediatric Outcomes Data Collection Instrument, the PedsQL Pediatric Pain Questionnaire, and the 10 meter Timed Walk. From data collected on these questionnaires, scales are formed that measure domains such as global functioning, extremity and physical function, transfers and basic mobility, sports/physical function, happiness, and pain/comfort. These QOL and pain measures will be given pre-surgery, 3 months, 6 months, and 12 months after surgery. Since the scales are continuous, summary statistics will be generated for each measure at each time-point. The paired t-test will be used to look at changes in these measures from pre-treatment levels through 12 months. Longitudinal data analysis methods will be used to evaluate long-term changes in these measure using regression techniques employing mixed models.

In order to determine factors which may be prognostic for the success of BMP-2 treatment, we will perform Wilcoxon Rank Sum Tests to within each group to compare:

- 1) age \leq 8 years versus age $>$ 8 years
- 2) prior surgery versus no prior surgery; and
- 3) prior rhBMP-2 exposure versus rhBMP-2 naïve.

Regarding dose of rhBMP-2, those with 4.2 mg of rhBMP-2 implanted will be compared to those with 8.4 mg of rhBMP-2 implanted with respect to success rate using a chi square contingency table and with respect to number of adverse events using the Wilcoxon Rank Sum Test.

Relationships between quality of life measures and other variables (i.e., pain) will be investigated using correlational analyses. Performance status will be assessed using the Karnofsky Performance Scale. Generalized linear models will be used to evaluate changes in these scales and scores over time.

Early Stopping Rule

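### The exploratory comparison of children with and without earlier rhBMP-2 exposure is confounded with prior surgery, so part of any prior-surgery effect could appear as an exposure effect

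*Combined protocol and SAP*

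**What the plan says.** Section 6.2 (Analyses) sets out a search for factors that may be prognostic for the success of BMP-2 treatment: "we will perform Wilcoxon Rank Sum Tests to within each group to compare" three pairs. The first is age at or below 8 years against above 8. The second is "prior surgery versus no prior surgery; and" the third is "prior rhBMP-2 exposure versus rhBMP-2" naïve. Each is a separate two-sample test, with no covariate and no restriction.

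Section 4.3 fixes who can be in these groups:

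- Which operations count: "Patients may be enrolled only at the time of 1st or 2nd surgery for tibial pseudarthrosis, not subsequent surgeries".
- When a re-operated child may enter: "Patients who have undergone 1 previous surgery for tibial pseudarthrosis repair will be eligible to enter the study if they have refracture".
- Where earlier exposure comes from: "Use of BMP-2 in the prior surgery is permitted, however patients with prior exposure must be screened for antibodies".
- How that exposure is handled: "Prior use of BMP-2 is allowed but will be recorded as a possible compounding factor".

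Section 5.8 (Antibody Studies) again places exposure in an earlier operation and says who is then removed: "Patients with history of prior exposure to BMP-2 in a previous surgery, who are positive for antibodies" before surgery are excluded.

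The plan also treats prior surgery as a factor that may matter for outcome. It is a stratification factor in the Randomized arm (Section 4.2.3), an imputation variable (Section 6.2, Missing data) and the second of the three comparisons. Nowhere is its expected size or direction given.

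**The concern.** Exposure is, in practice, nested in prior surgery. A child can be exposed only by having had an earlier operation, so the exposed group consists essentially of re-operated children, who must also have refractured to enter. The naïve group contains all first-operation children together with those re-operated without BMP-2. The third comparison therefore contrasts children who differ in exposure and, to a large extent, in operation number, and no analysis separates the two. Section 4.3 recognises prior use as a possible problem but provides only for recording it.

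What is at stake is the reading of an exploratory result. A poorer RUST score in exposed children could be taken as evidence about earlier BMP-2 when it reflects the previous operation and refracture. Equally, a real exposure difference could be masked. The primary comparison of BMP-2 with control does not depend on this test.

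**Working it through.** The plan gives no sample size, power or expected difference for this comparison, so it has no figure to reproduce. The scale for the illustration is taken from Section 6.2, and that part does reproduce. With midpoints 5.5, 8.5 and 11:

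- 33/42/25%: 5.5×0.33 + 8.5×0.42 + 11×0.25 = 8.135.
- 15/20/65%: 5.5×0.15 + 8.5×0.20 + 11×0.65 = 9.675.
- Difference 1.54, as stated. The probability that a child from the second distribution scores better (ties counted half) is 0.7015, against 0.702 in the plan's power table.

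**Step 1: how much passes through.** Suppose exposure has no effect and prior surgery shifts the mean (or success rate) by D. Exposed children carry the whole shift. In the naïve group only the re-operated part does. The expected exposed-minus-naïve difference is then s × D, where s is the first-operation share of the naïve group:

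s = first / (first + prior × (1 − fraction exposed)).

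The rank-sum effect behaves the same way: its departure from 0.5 is s times the departure between re-operated and first-operation children.

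**Step 2: values of s.** The mix is not in the documents. Assume half of the re-operated were exposed:

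- 20% with prior surgery: 0.80/0.90 = 0.89.
- 30%: 0.70/0.85 = 0.82.
- 50%: 0.50/0.75 = 0.67.

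The pilot data in Section 3.7 give a rough check on the first input. Of 24 children with a first rod-and-graft operation, 10 needed a second surgery, 4 of them amputations. First operations would then be 24/34 = 71% to 24/30 = 80% of the total, that is, 20–29% with prior surgery. If more than half of the re-operated were exposed, s would rise; if fewer, it would fall, but not below the first-operation share of the whole group (50–80% here).

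**Step 3: size on the RUST scale.** D is not given either. For illustration only:

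- D = 1.54 (as large as the planned treatment difference): 0.67×1.54 = 1.03 to 0.89×1.54 = 1.37 points of apparent exposure effect.
- D = 0.77 (half of that): 0.67×0.77 = 0.52 to 0.89×0.77 = 0.69 points.
- D = 0: none.

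**Step 4: how often the test would be significant.** Simulation for a BMP group of 26 (the maximum in Section 4.2.2), no true exposure effect, 200,000 runs, two-sided 0.05 (assumed, as the plan states no level for this test). First-operation children follow 15/20/65%. Re-operated children follow 33/42/25% (D = 1.54) or the average of the two (D = 0.77).

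| Re-operated (exposed + not) | First operation | s | Planned test, D = 1.54 | Restricted, D = 1.54 | Planned test, D = 0.77 | Restricted, D = 0.77 |
|---|---|---|---|---|---|---|
| 6 (3+3) | 20 | 0.87 | 20% | 3% | 10% | 4% |
| 10 (5+5) | 16 | 0.76 | 20% | 4.5% | 10% | 4% |
| 13 (6+7) | 13 | 0.65 | 16% | 5% | 8% | 5% |
| 18 (9+9) | 8 | 0.47 | 12% | 5% | 7% | 5% |

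Restricted means exposed against unexposed among re-operated children only. With D = 0 both versions reject in about 3–5% of runs. In the 5+5 case with D = 1.54 the expected spurious difference is 0.76×1.54 = 1.17 points for the planned test and zero for the restricted one.

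**The case against.** The case for leaving the plan alone has real substance.

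- **It is a screen for prognostic factors.** Section 6.2 makes no causal claim, one-factor-at-a-time tests are common for that purpose, and prior surgery is reported beside exposure. A reader might infer that the trial will report a prior-surgery effect as a BMP-2 effect. The documents do not support that: nothing says how the third test will be interpreted, and even with a large prior-surgery effect most simulated trials were not significant. What remains is that the estimate itself is shifted, whatever its p-value.
- **The prior-surgery effect is unknown.** Stratifying on a factor shows that it is suspected to matter, not that it does or in which direction. This stands, and the conclusion has to be conditional.
- **Nesting is inferred.** The bullet allowing prior BMP-2 use is not limited to tibial repair, and Section 2.2.2 describes a paediatric series, including children with NF1, in which 52 of 81 received rhBMP-2 in spine surgery. A child exposed elsewhere could be at a first tibial repair. Such exceptions would weaken the confounding slightly without removing it.
- **The third test is not simply the second repeated.** If half of the re-operated children are unexposed, they sit on the other side of the third comparison. At 50% with prior surgery, they form 0.25/0.75 = one third of the naïve group.
- **Sensitisation is assessed directly.** Serial antibody testing (Section 5.8) is the trial's evidence on that question, so a RUST comparison should not be given that role.
- **The restricted contrast is tiny.** This is true, and it is why the contrast should be descriptive. It does not make the unrestricted contrast answer the question.

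**Conclusion.** The point holds as a conditional one about an exploratory analysis. As written, the exposure comparison cannot be separated from prior surgery. If prior surgery affects RUST, a share of that effect equal to the first-operation share of the naïve group could appear as an exposure effect. That share is 67–89% if 20–50% of children have had prior surgery and half of those were exposed. It is not a prediction, because the documents give neither input. If prior surgery has no effect, there is no bias.

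The structural part rests on the text: exposure is described as arising in a previous surgery, and no section restricts, stratifies or adjusts the test. The size rests on the stated assumptions, and a naïve group made up mostly of first-operation children is a reasonable inference from the pilot data rather than a stated fact. The primary analysis is not affected. The change is worth making because it is cheap and needs no new data.

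**What to change.** In Section 6.2, replace the third comparison with: *among patients with one prior surgery, prior rhBMP-2 exposure versus no prior exposure*. Report it descriptively, as a difference with a confidence interval, and label it exploratory. Add a table of counts by prior surgery and prior exposure within each treatment group, which also shows how many exposed children sit in the prior-surgery side of the second comparison. If the all-patient comparison is kept, label it as confounded with prior surgery. Covariate adjustment would gain little, since the stratum without prior surgery has few or no exposed children.

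The cost is one clause and one small table, with no new data. The drawback is precision. On the assumptions above, the BMP group would have 26×0.20×0.5 = 2.6 to 26×0.50×0.5 = 6.5 exposed children, about 3–7. A control group of 10 would have 1.0 to 2.5. The intervals will be wide. Some selection also remains, because exposed children with positive antibodies are excluded before entry.

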5.2 Surgical Protocol for Treatment of Tibial Pseudarthrosis

The surgical protocol to be used is outlined in [name] et al. [2010] and includes tibial osteotomy with resection of the pseudarthrosis tissue, followed by placement of an intramedullary rod which provides rigid fixation. The exact type of rod used will vary based on availability in different centers and different countries, but will be a rigid rod similar in size and configuration to a Williams or Rush type rod. In no cases will the intramedullary canal be reamed. Fixation of the ankle will be at the discretion of the surgeon regardless of the patient's age. Bone grafting will be performed with autogenous bone from iliac crest placed into the excised pseudarthrosis site. As per instructions provided by the provider of the INFUSE® kit device (Medtronic), rhBMP-2 will be applied to an absorbable collagen sponge. The sponge is applied as an onlay, bridging the area of pseudarthrosis. The application of the collagen sponge saturated with rhBMP-2 is shown below.

Figure 5: Application of INFUSE at surgery.

FIG 1A.

FIG 1B.

The BMP-2 soaked collagen sponge is placed around bone junction at the tibial osteotomy site. After autogenous bone graft has been placed in the tibial osteotomy site, the collagen sponge is wrapped around both the tibia and the bone graft.

The dosing of rhBMP-2 is restricted to the size of absorbable collagen sponge used in the surgical field. The concentration of rhBMP-2 in the sponge is standardized to 1.5 mg/cc sterile water on the sponge. For the purposes of this trial, the size of INFUSE bone graft used will be adjusted for weight. Patients less than 30 kilogram weight will receive a small INFUSE package (4.2mg of rhBMP-2 on 2 collagen sponges, with concentration of 1.5 mg/cc); those greater than or equal to 30kg weight will receive a medium INFUSE package (8.4 mg BMP-2 and 4 collagen sponges, with concentration of 1.5 mg/cc). Higher doses were avoided due to the concern that higher doses of rhBMP-2 can induce osteoclasts that initiate bone resorption, and to decrease theoretical risk of carcinogenicity possibly seen with very high doses of BMP-2.

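### The planned 4.2 mg v 8.4 mg comparison is fully confounded with body weight (under 30 kg v 30 kg or more), so it cannot support a conclusion about dose in either direction

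*Combined protocol and SAP*

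**What the plan says.** The Analyses part of section 6.2 has one sentence on rhBMP-2 dose. It says that "those with 4.2 mg of rhBMP-2 implanted will be compared to those with 8.4 mg of rhBMP-2 implanted", first "with respect to success rate using a chi square contingency table" and then "with respect to number of adverse events using the Wilcoxon Rank Sum Test". It states no significance level, covariate, stratification or rule for interpreting a difference.

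Section 5.2 says how a patient comes to be in one group or the other: "For the purposes of this trial, the size of INFUSE bone graft used will be adjusted for weight". The rule is a single cut-off. "Patients less than 30 kilogram weight will receive a small INFUSE package (4.2mg of rhBMP-2 on 2 collagen sponges", while "those greater than or equal to 30kg weight will receive a medium INFUSE package (8.4 mg BMP-2 and 4 collagen sponges". Strength is the same in both kits: "The concentration of rhBMP-2 in the sponge is standardized to 1.5 mg/cc sterile water on the sponge". The groups therefore differ in total amount and number of sponges, not in concentration. The summary list in section 5.2 repeats the rule.

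Elsewhere the plan treats age as relevant to outcome. It is a randomization stratum (section 4.2.3), an imputation variable (section 6.2, Missing data) and one of three factors to be tested within each treatment group (section 6.2, Analyses). The age test is separate from the dose comparison and is not crossed with it.

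**The concern.** A comparison of two doses is informative only if patients who could have received either dose are found in both groups. Here there are none. Eligibility runs from 2 to 18 years (section 4.3), so a 30 kg cut can be expected to split the BMP patients largely into younger and older children, with smaller and larger tibias. A difference in healing or adverse events between the kits could come from dose, weight, age or bone size. A finding of no difference could equally hide a dose effect and an age effect that cancel.

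The question is not idle in this trial. Section 5.2 says higher doses were avoided because of concerns about bone resorption and carcinogenicity, and safety is one of the primary aims (section 2.3). A result presented under the label of dose would bear on those concerns, and the design cannot supply that evidence.

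**Working it through.** **The plan's own figure.** The documents give no sample size, effect size or power for this comparison, so there is nothing to reproduce. The check sets the dosing rule beside the analysis and then illustrates the size of the effect.

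**Step 1: who can be in each group (section 5.2).**

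| Weight | 4.2 mg | 8.4 mg |
|---|---|---|
| Under 30 kg | all | none |
| 30 kg or more | none | all |

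Write success as a + b·(8.4 mg kit) + c·(30 kg or more). The two indicators are identical for every patient dosed by protocol, so only the sum b + c can be estimated. The chi-square and Wilcoxon tests both test that sum. Adding weight as a continuous covariate does not help, because the weight ranges do not overlap and any separation would be extrapolation across the cut. Adjusting for age would still leave weight.

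**Step 2: how often confounding alone gives a significant result.**

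Inputs from the documents:
- At most 26 BMP patients (section 4.2.2).

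Assumptions, because the documents give none of these:
- the split of the 26 at 30 kg;
- the success rates in the two weight groups;
- a two-sided 0.05 level for this test.

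True dose effect: zero. With x successes among n1 patients under 30 kg and y among n2 at or above 30 kg, let p = (x + y)/26. The uncorrected statistic is

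X² = (x/n1 − y/n2)² / [p(1 − p)(1/n1 + 1/n2)],

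significant when X² > 3.8415. The probability of significance is the sum of the two-binomial probabilities over all significant (x, y).

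| Success under 30 kg v 30 kg or more, from age or size alone | Split 20:6 | Split 13:13 |
|---|---|---|
| 50% v 80% | 25% | 41% |
| 55% v 70% | 9% | 15% |
| 60% v 70% | 6% | 10% |
| 65% v 65% (no difference) | 5% | 6% |

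For 50% v 80% with a 16:10 split the figure is 34%.

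**Step 3: adequacy of the chi-square approximation.** Section 6.0 anticipates younger children, so a small upper-weight group is plausible. For 20:6 at 50% v 80%:
- pooled success = (20 × 0.50 + 6 × 0.80)/26 = 14.8/26 = 56.9%;
- expected successes in the group of 6 = 6 × 0.569 = 3.4;
- expected failures = 6 × 0.431 = 2.6.

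Both are below 5.

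**The case against.** Four points can be made for the plan.

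- **The plan does not claim a dose effect.** A reader might infer that any difference will be reported as one. The documents do not say so. They label the comparison as being about dose and say nothing on interpretation. What stands is that the label is there and a caution is not.
- **Age is examined separately.** The age test (8 or under v over 8) is run within each treatment group, so also in controls, where it gives some indirect evidence on whether age predicts healing without BMP-2. That is useful, but it is not crossed with kit size and cannot separate dose from size.
- **The illustration depends on assumptions.** The 25% to 41% needs an assumed 30-point difference in success from age or size. For a 10-point difference (60% v 70%) the rates are close to those with no difference at all. A reader should not take the upper figures as the expected error rate. The confounding in Step 1 depends on none of these figures.
- **Dose per kg might seem a way out.** It is not. Within each kit it is a fixed amount divided by weight, so it is still determined by weight. Nor do the documents make it the relevant exposure for a locally applied device at fixed concentration.

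It is also fair that this is one sentence about at most 26 patients. It feeds neither the primary Wilcoxon comparison nor the early stopping rules.

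**Conclusion.** The point holds. By the protocol's own dosing rule, dose group and weight group coincide exactly, and the planned unadjusted tests cannot attribute a difference, or the lack of one, to dose. This rests on the text of sections 5.2 and 6.2 alone and assumes only that dosing follows the protocol. How often a spurious significant result would arise depends on how strongly age or size affects healing, which the documents do not give. Over the range shown it runs from hardly above the nominal rate to about 41%. The consequence is confined to a minor secondary analysis.

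**What to change.** Change the analysis text only; nothing here concerns the dosing rule.

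1. In section 6.2, describe the analysis as a descriptive comparison of weight/kit groups (under 30 kg v 30 kg or more), and state that it cannot separate dose from weight or age.
2. Show the same weight split in the control arm, and give the BMP-minus-control difference within each weight group with confidence intervals. Controls receive no BMP-2, so their split shows the weight or age effect without it. State two limits. Controls may number as few as 10 (section 4.2.2), so cells may be very small. A difference between weight groups could also mean that BMP-2 works differently by age or size.
3. Use Fisher's exact test instead of chi-square for success. This deals with the small counts, not with the confounding.

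The cost is a few lines of wording and one extra table. Weight is already collected (section 5.8 and Appendix I). The downside is that the trial no longer offers an answer on dose, which its design could not give.

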4.2.2 Recruitment

The primary recruitment for this study will be through participating NF Consortium Centers and orthopaedic centers. This prospective clinic trial will be posted on websites and included in the newsletters of the NF support organizations (CTF and NF Network). Directors and coordinators at each of the 42 clinics affiliated with the CTF NF Clinic Network will be notified of the trial and eligibility.

A total of between 36-52 patients will be enrolled prospectively in this trial. The maximum number of patients that will be enrolled in the BMP arm is 26, based on the numbers of Infuse kits supplied by the sponsor. The ideal number of Control patients is also 26, but may range from 10-26, based on preferences of enrollees. This is further discussed in the Study Modification section below, 4.2.3. We expect that dropout rate of participants, once they have been enrolled and had their surgical procedure performed, should be very low, in the range of 5%. The experience of participating surgeons is that their TPA patients who have had surgery are extremely likely to attend subsequent follow-up visits. The final endpoint of the trial is at the one-year assessment of the last patient enrolled. Due to slow enrollment in the first year of the trial, we have added 5 Shriners orthopedic centers in the U.S. as participants in the trial. Funding has been included to help support family travel as outlined, in the Informed Consent forms (range of \$200-\$500 per patient, with the greater amount for patients living further than 50 miles from the participating center). Participants who live further than 50 miles from a participating center may have an option to elect to have several of the follow-up visits and Xrays (3 and 9 months post-op) performed by their local orthopedic surgeon, with results sent to the DMAC and radiographic team at TSRH. However, the surgical procedure and follow-up visits at 6 and 12 months must be at a participating center with either the orthopaedic surgeon or the NF specialist. All centers performing any subject evaluations for the study must have completed the appropriate mandatory electronic training modules prior to performing any assessments.

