While BMP-2 has been evaluated extensively in non-NF1 patients, it has not been administered as a clinical trial in children with NF1 who have tibial pseudarthrosis. An early stopping rule will be invoked to prevent accrual of patients onto the study in the event that BMP-2 is associated with a higher than acceptable rate of severe toxicity identified at 6 weeks and 12 weeks post surgery [types: Grade 3 opportunistic infection, Grade 4 rash, Grade 3 hypertension, grade \geq 3 allergic reaction (determined by clinical assessment and antibody levels), grade 3 renal toxicity, severe ectopic bone formation requiring surgery, or the development of malignant peripheral nerve sheath tumor or other cancers]. Toxicity assessment will be graded according to the National Cancer Institute Common Terminology Criteria for Adverse Events (CTCAE) (v4.03). After 10 patients are enrolled in each arm, toxicity will be reviewed and if greater than the

number of patients shown in the table below experiences severe toxicity, accrual will be stopped. Based upon results calculated using the binomial distribution, the following holds true for the table as a whole:

True probability of toxicity	Chance of stopping early
.10	7%
.20	32%
.25	47%
.30	62%
.40	83%

Number of patients	Trial will be stopped if the number of patients with severe toxicity is greater than or equal to the number below
10	3

Should the number of patients showing severe toxicity during treatment with BMP-2 exceed 25% of the total number of patients enrolled, the study committee and medical monitor will review the toxicities and define whether a protocol revision is required. This 25% level was determined based on prior studies showing a total complication rate of 17% in pediatric patients treated with BMP-2 [[name] and [name], 2010].

Likewise, the trial may be stopped early if at least 6 patients of the first 10 enrollees in the BMP-2 arm have complete failure of union by 12 months postop (RUST score of 5 or less). This will be determined after the first 10 enrollees in the BMP-2 arm have completed the 12 month assessment. The entire study will be terminated if the BMP-2 group is stopped early due to toxicity or failure of union.

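### The BMP-2 toxicity review waits for 10 patients in each arm, so under the Choice design a slow control arm can delay it, and the text does not say which patients the limit of 3 covers

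*Combined protocol and SAP*

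**What the plan says.** The Early Stopping Rule in Section 6.2 is meant to halt accrual if BMP-2 shows a "higher than acceptable rate of severe toxicity identified at 6 weeks and 12 weeks post surgery". Its trigger reads: "After 10 patients are enrolled in each arm, toxicity will be reviewed". The prose then stops accrual if the count is greater than the tabled number. The table has one row (10 patients, limit 3), and its header says: "Trial will be stopped if the number of patients with severe toxicity is greater than or equal to the number below". The stopping chances are 7, 32, 47, 62 and 83% at true rates of .10, .20, .25, .30 and .40, introduced with "Based upon results calculated using the binomial distribution".

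The failure-of-union rule in the same section is keyed differently: "This will be determined after the first 10 enrollees in the BMP-2 arm have completed the 12 month assessment".

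On enrolment, Section 4.2.2 caps the BMP arm at 26 and says of controls: "The ideal number of Control patients is also 26, but may range from 10-26, based on preferences of enrollees". The end of Section 6.2 sets a minimum goal of 15 controls with 26 BMP patients. Sections 4.2.3 and 6.2 expect more families to prefer BMP. The initial plan was 25 per group.

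**The concern.** A trigger of 10 per arm suits two arms that fill at the same pace, as in the initial 25-per-group plan. Under the Choice design the arms need not fill together, and the plan expects controls to lag. The review exists to limit children's exposure to BMP-2, yet its date can depend on how quickly families accept surgery without BMP-2.

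Three further points are open:
- The trigger counts patients enrolled. Enrolment precedes surgery (Section 4.2.3), so the most recent patients may have no 6- or 12-week data, and no pause in accrual is stated.
- When more than 10 BMP patients are present, the text does not say whether the limit of 3 applies to the first 10 or to all of them.
- The prose and the table differ on whether exactly 3 events stops the trial.

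At stake are the number of implants the rule can still prevent and whether its error rates are those printed.

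**Working it through.** **1. The printed table.** Inputs from Section 6.2: 10 patients, stop at 3 or more. P(X ≥ 3) with X ~ Binomial(10, p). At p = .10 this is 1 − (.3487 + .3874 + .1937) = .070. All five rates give 7.0, 32.2, 47.4, 61.7 and 83.3%, so the printed figures reproduce.

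**2. The prose limit.** More than 3 means 4 or more of 10. P(X ≥ 4) = 1.3, 12.1, 22.4, 35.0 and 61.8%. These do not match the printed figures; the table's wording does.

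**3. The limit of 3 applied to all BMP patients present at the trigger.**

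| BMP patients counted | p = .10 | p = .20 |
|---|---|---|
| 10 (as printed) | 7% | 32% |
| 16 | 21% | 65% |
| 24 | 44% | 89% |

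**4. BMP patients enrolled when the trigger is met.** Inputs: 26 BMP patients and c controls (Sections 4.2.2 and 6.2). Assumption: enrolment order is random. The expected number of BMP patients before the 10th control is 26 × 10/(c + 1). For c = 10 this is 260/11 = 23.6; for c = 15 it is 260/16 = 16.25. The trigger also needs at least 10 BMP patients, so the mean count at the trigger was simulated (20,000 orders for each c).

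| Controls | Mean BMP at trigger | More than 13 BMP | Exactly 10 BMP |
|---|---|---|---|
| 10 | 23.6 | 99.6% | 0.1% |
| 12 | 20.0 | 95% | 1.2% |
| 15 | 16.4 | 76% | 8% |
| 20 | 12.9 | 38% | 32% |
| 26 | 11.2 | 13% | 62% |

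All 26 BMP patients precede the 10th control only if the last c − 9 patients enrolled are all controls. For c = 10 the chance is 10/36 = 28%. For c = 12 it is C(12,3)/C(38,3) = 220/8,436 = 2.6%. For c = 15 it is C(15,6)/C(41,6) = 5,005/4,496,388 = 0.1%.

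**5. The follow-up lag.** Table 2 in Section 4.2.1 lists 90+ surgeries per 4 years. Taking 90, that is 90/4 × 12/52 = 5.2 per 12 weeks over both arms if every case enrolled. The lag adds a few patients; the each-arm condition is the larger effect.

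**6. The 25% review.** Section 6.2 also calls for committee and medical-monitor review if severe toxicities on BMP-2 exceed 25% of the total enrolled. Read literally, with 24 BMP patients and 10 controls, 25% of 34 is 8.5. Nine toxicities are then needed, which is 9/24 = 37.5% of BMP patients.

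**The case against.** The printed probabilities are right for the row they describe. A reader might infer that they do not apply to this trial. The documents do not support that: they hold if the limit is applied to the first 10 BMP patients at 3 or more. The difficulty is that the text never states this condition.

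A reader might also infer that most or all BMP-2 children will be treated before any review. That depends on a low control count. With 20 to 26 controls the trigger falls at about 11 to 13 BMP patients, and even with 10 controls all 26 come first in only 28% of orders. The power table goes down to 5 controls, where the trigger would never be met, but that lies below the planned minimum of 36 patients (26 + 10).

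Random order may also overstate the delay. The Choice option was added after the first year, earlier patients entered a design planned at 25 per group, and randomised patients now go 3:2 to control. Early balance would bring the 10th control forward. First-year numbers are not given, so this cannot be sized.

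Finally, the trial has other oversight: the 25% review, an independent DSMB, a research monitor with authority to stop (Section 6.4), and expedited reporting within 24 hours (Section 5.9). It would be wrong to infer that nobody looks at safety before the trigger.

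These points limit the size of the concern but leave its core. The low-control case is the one the modification was written to handle, and at the plan's own goal of 15 controls the expected count is about 16 of 26. The 25% review is diluted by its denominator and leads only to a committee review, and Section 6.4 gives the DSMB and monitor no numeric limit. *Arm* also denotes Choice versus Randomized in Section 4.2.3, which adds a further ambiguity.

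**Conclusion.** The concern holds in conditional form. The each-arm trigger can make the pace of control enrolment decide when BMP-2 toxicity is reviewed: at about 24, 16, or 11 to 13 of 26 BMP patients with 10, 15, or 20 to 26 controls. Counting enrolment does not ensure that the 6- and 12-week data exist. The stated operating characteristics hold only for 3 or more events among exactly 10 BMP patients. Other readings that the text leaves open move the stopping chance at a true rate of .10 from 7% to anywhere between 1.3% (the prose limit) and 44% (3 or more of 24).

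The counts rest on random enrolment order and on reaching 26 BMP patients. The documents give no preference share, so the control count is shown as a range. This should be fixed. It leaves this rule unreliable, not the trial without safety oversight.

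**What to change.** In Section 6.2:
- Tie the toxicity review to the first 10 BMP-2-treated patients who have completed the 12-week assessment, regardless of the number of controls.
- State that the tabled limit applies to those 10 patients.
- Reconcile *greater than* in the prose with *greater than or equal to* in the table. The printed probabilities match the table's version.

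This keeps the plan's own number of patients, tabled limit and toxicity list, makes the printed 7/32/47/62/83% the rule's actual properties, and follows the form of the failure-of-union rule. Up to 26 − 10 = 16 BMP-2 implants would remain avoidable, fewer if accrual continues while the 12-week visits are completed.

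The cost is a sentence or two and no new data. Fewer control data would be available for context at the review. With near-equal arms, waiting for 12-week visits could put the review slightly later than the present trigger, so the change should not be described as always bringing it forward.
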